#### 2.3.3. Treatment Period and Monitoring

The follow up visits will take place in various outpatient clinics and/or procedural areas throughout the University of Pittsburgh Medical Center (UPMC) Presbyterian Hospital, UPMC Montefiore Hospital, Kaufmann Building, and/or Falk Clinic. The intravenous glucose tolerance test (IVGTT) will be performed at the Montefiore Clinical and Translational Research Center (CTRC).

Phone Visits: Weeks 4 and 8 (+/- 7 Days) following the start of each treatment arm

- Interval history (ER visits/hospitalizations)
- · Review of concomitant medications
- Review for compliance and symptoms
- AE/SAE assessment

## \*\*\*If the PI deems it necessary to bring a participant to clinic, the following will be performed in addition to the items listed under the Phone visits:

These visits may take up to 2 hours to complete. Subjects will be instructed to hold the morning or afternoon dose of study drug depending on the appointment time.

- Self-administration of drug by subject under direct supervision of study team
- Interval history
- Physical examination including vital signs, pulse co-oximetry, and body weight
- Methemoglobin percentage level via co-oximetry (approximately 30-45 minutes post study medication)
- Review of concomitant medications
- Collection of used study drug and diary; review for compliancy and symptoms
- Functional Class assessment
- NT-proBNP blood sample. The total volume of blood drawn for this sample is approximately 1 teaspoon.
- 6MWT and Borg scale
- Dispense study drug and new diary cards (if needed)
- AE/SAE assessment

#### Clinic Visit Week 10 (+/- 14) and End of Treatment (+/- 14) to begin testing visits)

These visits may take up to 4 days to complete all the assessments. Subjects e instructed to arrive in a fasted state and hold study medication the morning of these scheduled visits. Participants will take their morning or afternoon dose under direct supervision of the study team and will continue to take the study medication TID until all testing is completed.

- Self-administration of drug by subject under direct supervision of study team at the start of each visit
- Interval history
- Physical examination including vital signs, pulse co-oximetry, and body weight
- Waist measurement
- Methemoglobin percentage level via co-oximetry (approximately 30-45 minutes post study medication)
- Review of concomitant medications
- Collection of used study drug and diary; review for compliancy and symptoms
- Functional Class assessment
- 6MWT and Borg scale
- Accelerometer
- Urine pregnancy if applicable
- Echocardiogram

- Sponsor: [name]
- Blood samples: fasting glucose, comprehensive metabolic panel, hemoglobin A1C, fasting lipid profile, PT/PTT, complete blood count, platelet and differential, and NT-proBNP. The total volume of blood drawn for these samples is approximately 1 ½ tablespoons (20 mL).
- Cardiopulmonary exercise test (CPET): Constant Work Rate Test
- RHC: Hemodynamic measurements will be completed at rest. Once the resting measurements are completed, the patient will take a single dose of their randomly assigned study medication. Another set of hemodynamic measurements will be taken approximately 30-45 minutes after the study medication is taken. Following these measurements, the patient will complete a constant workrate supine exercise test lasting about 4-12 minutes. Patients will pedal until exhaustion. The information collected from the baseline constant workrate exercise test during the baseline procedures will determine the watts used for the constant workrate supine exercise tests in the catheterization lab during weeks 10 and EOT. Hemodynamic measurements will be taken about every 2 minutes during the exercise test.
- Micromanometry (optional) during RHC
- Research blood samples (plasma nitrite concentrations, red cell iron-nitrosyl-hemoglobin, and platelet studies) during RHC: pre-dose and approximately 30-45 minutes post dosing of study drug. The total volume of blood drawn is approximately 1 /4 tablespoons (26 mL).
- AE/SAE assessment
- IVGTT (optional)
- Completion of the KCCQ, SF-36 and PAH-SYMPACT Questionnaires
- Once all of the testing is completed, subjects will be given a diary card to keep track of any symptoms during the 2-week washout period and again after the EOT testing for the 30 day follow up phone call.

## 2-Week Washout Period (+ 7 days)

Upon completion of the first 10 weeks of study treatment, a 2-week washout period will occur. Subjects will not receive the study drug or placebo for two (2) weeks. Subjects will be given a diary card to keep track of any symptoms, doctor appointments, etc. during this time period. Subjects will return to clinic after the washout to cross over to alternative therapy and undergo the same study procedures as the first 10 weeks.

## **Cross-Over Visit**

This visit may be completed over 2 days dependent on patient and staff availability. Subjects will be instructed to fast for a minimum of 8 hours on the day of the bloodwork. Patients will only need to fast for 2 hours prior to the constant work rate exercise test.

- Self-administration of drug by subject under direct supervision of study team
- Interval history
- Collection of diary; review for compliancy and symptoms
- Physical examination including vital signs, pulse co-oximetry, and body weight
- Urine pregnancy if applicable
- Methemoglobin percentage level via co-oximetry (approximately 30-45 minutes post study medication)
- Review of concomitant medications
- Functional Class assessment
- 6MWT and Borg scale
- Constant work rate exercise test
- Accelerometer

- Sponsor: [name]
- Blood samples: fasting glucose, comprehensive metabolic panel, hemoglobin A1C, fasting lipid profile, PT/PTT, complete blood count, platelet and differential, NT-proBNP, research blood samples: plasma nitrite concentration, red cell iron-nitrosyl-hemoglobin, and platelet studies. The total volume of blood drawn for these samples is approximately 2 ½ tablespoons (35 mL).
- Dispense study drug and diary cards
- AE/SAE assessment
- Completion of the KCCQ, SF-36 and PAH-SYMPACT Questionnaires

Weekly phone follow-up (+/- 7 days) assessments will occur while on active study treatment (when subjects are not followed up in clinic) that will include symptom review, assessment of adverse events, review of concomitmant medications, and interval histories. Subjects will return to clinic at week 10 and undergo study procedures as noted in the first 10 weeks.

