## **Randomization**

Randomization to study drug verses placebo will occur upon completion of all screening and baseline procedures and confirmation by a study physician that subjects have met all eligibility criteria. Randomization of sequence of nitrite-placebo versus placebo-nitrite followed by cross-over to the alternative treatment in a 1:1 ratio according to a computer generated pseudo-random code.

Subjects will self-administer their first dose of study medication or placebo under supervision of the physician investigator or the primary study coordinator after eligibility has been confirmed. Each patient will have their vital signs and methemoglobin measured before taking the study medication and approximately 30-45 minutes after taking their first dose.

Subjects will also be dispensed their study medication for home use including a medication administration diary. Subjects will return the previously dispensed study medication and diary at every study visit thereafter, and medication compliance will be assessed.

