## 2.8 STATISTICAL ANALYSIS

#### 2.8.1 Sample Size and Power

**Sample size:** Prior study has indicated that oral nitrate reduces baseline mean PAP -7 (SD = 4) mm Hg vs. -3 (4) mmHg in placebo group. A sample size of 12 in each group provides 88%

power to detect this difference. This sample size will provide 80% power to detect -10 (6) vs. -5 (6) decrease in post-exercise mPAP in treatment and placebo group, respectively.

**Statistical analysis:** Pre-randomization characteristics of two groups will be presented using the median (interquartile range) or frequency tables at each study sequence. The difference of mPAP during submaximal exercise as compared between placebo and nitrite at 10 weeks (i.e. the week 10 RHC of placebo vs week 10 RHC of nitrite) using the parametric PK-cross analysis (i.e. an ANOVA which determines the sequence, period, carryover, and treatment effects). Post-exercise values of before and after crossover will be compared between two groups using similar approach. For secondary outcomes, we will compare the difference of baseline and follow-up value and compare these differences with a parametric test. Alternatively a nonparametric test will be used for these comparisons. For both primary and secondary outcomes, treatment effect in each sequence as well as mean (SD) total treatment effect and corresponding P values will be reported.

We will also test the effect of treatment on pre-exercise mPAP and secondary outcomes using mixed effect models. In all analysis, missing data will be imputed and sensitivity analysis with imputed data will be performed. All analyses will be performed by ITT approach.

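### The cross-over visit allows the post-washout tests to follow the first period-2 dose, so a period-2 baseline taken there for secondary outcomes can already contain drug effect

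*Combined protocol and SAP*

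**What the plan says.** Section 2.3.3, under Cross-Over Visit, opens its list with "Self-administration of drug by subject under direct supervision of study team". Further down come a methemoglobin reading 30-45 minutes after the dose, functional class, the 6MWT with Borg score, the constant work rate (CWR) test, accelerometer, bloods (including fasting glucose, NT-proBNP and plasma nitrite) and questionnaires. Methemoglobin is the only item timed against the dose. The section adds: "This visit may be completed over 2 days dependent on patient and staff availability".

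For period 1, section 2.3.2 states: "Randomization to study drug verses placebo will occur upon completion of all screening and baseline procedures". The first blinded dose follows randomization.

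For the analysis, section 2.8.1 says of secondary outcomes: "we will compare the difference of baseline and follow-up value and compare these differences with a parametric test". It does not say which visit supplies the baseline for period 2. Sections 2.4.5 and 2.4.6 name the cross-over visit as a time point for the CWR test and for comparison of the blood results.

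**The concern.** A change-from-baseline analysis in a two-period trial needs a baseline free of the treatment about to be studied. The cross-over visit is the natural source for period 2, since no other efficacy assessment falls between the end of washout and the start of period-2 treatment. If the tests there follow a capsule, subjects crossing to placebo have an unexposed baseline and subjects crossing to nitrite have an exposed one.

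An acute effect is plausible on the plan's own account. Hypothesis 1 in section 1.2 expects one 40 mg dose to act on the pulmonary circulation and on filling pressures. The background in section 1.3.1 cites longer exercise duration in HFpEF after a single dose of nitrate. Subtracting an acute benefit would pull the secondary results towards no difference. It would also make the two sequences differ for a reason unrelated to carry-over.

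**Working it through.** No figure in the plan is at issue. The check compares the text, then illustrates the size.

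**1. Dose timing at each visit**

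| Visit | What is stated about the dose |
|---|---|
| Screening (2.3.1): 6MWT, NYHA class, routine bloods | Can include an open-label 40 mg dose. Only methemoglobin and the research samples are timed before and after it |
| Baseline (2.3.2): CWR test, questionnaires | Completed before randomization and the first blinded dose |
| Week 10 and end of treatment (2.3.3) | Dosing listed first: "Self-administration of drug by subject under direct supervision of study team at the start of each visit". Research samples: "pre-dose and approximately 30-45 minutes post dosing of study drug" |
| Cross-over (2.3.3) | Dosing listed first. Only methemoglobin is timed, after the dose |

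The plan gives pre-dose and post-dose times for research samples at other visits and gives none at cross-over. On a two-day visit with dosing on day 1, every day-2 test is post-dose.

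**2. Outcomes exposed**

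Secondary endpoints in section 2.6.2 that are also measured at cross-over (Table 1): 6MWT with Borg score and saturation, NYHA class, NT-proBNP, fasting glucose, nitrite metabolites and CWR endurance time. The questionnaires are collected there too but are not listed endpoints.

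Not exposed:
- The primary endpoint compares one week-10 catheterization with the other (2.6.1).
- Catheterization, echocardiography and the glucose tolerance test are not done at cross-over.
- The isotime window is set by the week-10 and end-of-treatment tests (2.4.5).
- Slow markers such as HbA1c would barely move after one dose.

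**3. Size, if the cross-over visit is the period-2 baseline**

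Let d be the true 10-week effect and a the fraction of it already present when the period-2 baseline is measured. The value of a is assumed. Take no period effect, no true carry-over and an unexposed period-1 baseline. Mean changes from the period baseline are:

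- nitrite then placebo: d, then 0
- placebo then nitrite: 0, then (1 - a)d

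Period-1 difference = d. Period-2 difference = (1 - a)d. Combined estimate = [d + (1 - a)d]/2 = d(1 - a/2). The sequence totals are d and (1 - a)d, so they differ by a·d.

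| a (assumed) | Period-2 difference / d | Combined estimate / d | Sequence difference / d |
|---|---|---|---|
| 0 | 1.00 | 1.000 | 0 |
| 0.25 | 0.75 | 0.875 | 0.25 |
| 0.50 | 0.50 | 0.750 | 0.50 |
| 0.75 | 0.25 | 0.625 | 0.75 |
| 1 | 0 | 0.500 | 1.00 |

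**4. If one pre-randomization baseline B serves both periods**

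With Y1 and Y2 the follow-up values, (Y1 - B) - (Y2 - B) = Y1 - Y2. The baseline cancels within subject and this bias is zero.

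**The case against.** The strongest reply is that a bulleted list is not a timeline. The week-10 list also puts dosing first, and even places it at the start of the visit, yet it has resting catheterization measurements and the first research sample taken before the dose. The cross-over list lacks the words about the start of the visit and puts dispensing after the tests. This stands. A reader might infer that the protocol requires post-dose testing at cross-over, but the text only permits and suggests it.

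Second, a reader might infer that every period-1 baseline is clean and every period-2 baseline is not. The documents do not support that. The clear contrast is limited to the CWR test and questionnaires. The period-1 6MWT, NYHA class and routine bloods come from screening, where an open-label dose can be given and their timing against it is not stated.

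Third, section 2.8.1 never says that cross-over values are subtracted. Treating that visit as the period-2 baseline is a strong inference from its place after washout and its naming as a comparison time point, but it remains an inference.

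Fourth, the support for an acute effect is indirect. Hypothesis 1 concerns hemodynamics that are not measured at cross-over. The exercise evidence concerns nitrate, in HFpEF without pulmonary hypertension. The percentages in the table are therefore algebra on assumed fractions and do not measure a bias.

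Finally, a reader might say that post-dose plasma nitrite defeats a check of washout. No section gives the cross-over sample that role, so the point does not rest on it.

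**Conclusion.** The concern holds in limited form and should be corrected. The cross-over section leaves open, and by its order invites, testing after the first period-2 dose, at the only efficacy assessment between washout and period-2 treatment. If that visit is the period-2 baseline, the secondary outcomes measured there can be biased towards no difference through subjects who receive nitrite second. The sequences would then differ by a·d. Section 2.8.1 plans to report the treatment effect in each sequence, and a model like the primary ANOVA could take this difference for carry-over.

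The combined estimate would be (1 - a/2) of the true effect: 87.5%, 75% and 62.5% for assumed a of 25%, 50% and 75%. The documents give no value for a. The result rests on three conditions: sites dose before testing, the cross-over values are subtracted, and one dose moves the outcome in question. If any of them fails, this bias is absent.

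A reader might extend the concern to the trial's main conclusion. The documents rule that out, because the primary mPAP contrast uses no cross-over measurement.

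**What to change.** - **Cross-Over Visit, section 2.3.3.** State that the 6MWT with Borg score, CWR test, functional class, bloods and questionnaires are completed before the first period-2 capsule, and that only the post-dose methemoglobin check follows it.
- **Screening, section 2.3.1.** Apply the same pre-dose order to the 6MWT, functional class and bloods when the open-label dose is given, so that both periods use the same kind of baseline.
- **Section 2.8.1.** Name the visit that supplies the period-2 baseline for each secondary outcome.
- **Visits already held.** Record the time from dose to test where it is known, and add a sensitivity analysis that does not use the period-2 baseline.

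Accelerometry should stay outside this rule. The device is worn for about 7-10 days, so starting it before the capsule would not give an unexposed recording.

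The cost is small: the order of procedures within existing visits changes and no test is added. On two-day cross-over visits, the first dose and dispensing move to the end.

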## 2.3.4. End of Trial and Follow-Up Period

Post Study Drug Telephone Assessment (approximately 30 days after the final day of testing)

• Telephone assessment for interval histories and AEs.

## 2.3.5. Open Label Period

Upon completion of the end of treatment visit, subjects will be given the option to receive open-label drug for 6 months. Subjects will receive open-label of Oral Nitrite  $(N0_2^-)$ . Subjects may be asked to return monthly for blood pressure, methemoglobin checks (optional). Oral nitrite will be dispensed at each of these visits. Patients will be asked to return in-person for month 3 and month 6 of the open label period, and will be asked to complete 3 questionnaires (KCCQ, SF-36, and PAH-SYMPACT), perform a six-minute walk test, and have a blood collection to measure NT-proBNP level. The total amount of blood drawn is 4ml.

Currently HFpEF is a disease with no approved treatments. The main purpose of the open label period is to provide specific treatment to those patients that have a response during the crossover trial. This can also be a benefit to the patients if they are getting relief from their symptoms from the oral nitrite. It will also provide longer term safety data. Patient reported outcomes such as QOL are collected.

## 2.3.6. Schedule of Assessments

The table below summarizes the protocol procedures that will be performed throughout the study trial TABLE 1

TABLE 1										
Study Phase	Screening	Baseline	Weekly Phone Call +/- 7 days	Weeks 4 and 8 (per Pl only) +/- 7 days	Week 10 +/-14 days	Cross- over Visit	Weekly Phone Call +/- 7 days	Weeks 4 and 8 (per Pl only) +/- 7 days	End of Treatment (EOT)	Follow-up Period Phone Call
Informed Consent	X									
I/E Criteria	X									
Medical History &	Х									
Demographics	v			V	v	V		V	V	
Physical Exam	X	Х		X	X	X		X	X	
Vital Signs & Body Weight		Χ								
Oxygen Saturation	X			X	X	X		X	X	
Blood Samples: fasting glucose, CMP, hemoglo bin A1C, fasting lipid profile, PT/PTT, complete blood count, platelet and differential, research labs	X				х	X			х	
α NTproBNP blood test	Х			Х	Х	Х		Х	Х	
Urine Pregnancy test (if applicable)	X				X	X			x	
NYHA functional class assessment	Х			X	X	X		х	X	
α 6 minute walk test (6MWT)	Х			Х	Х	Х		Х	Х	
Echocardiogram	X∞				Х				х	
Spirometry lung	X.	Х							Α	
function test										
Incremental exercise testing (IET)		Х								
Practice Constant Work Rate (CWR P )		Х								
Constant Work Rate (CWR) test		Х			Х	Х			Х	
(RHC): RA, RV, PA, PCWP, CO/CI Resting hemodynamics and (sub-maximal exercise at Week 10 and EOT only)	Χ †				х				Х	
Micromanometry     (optional)	X				X				X	
Accelerometer		Х			Х	Х			Х	
л IVGTT					Х				X	
MetHgb levels via co-	Х	Х		Х	Х	Х		Х	X	
oximetry		v								
Randomization Dispense and study		X		X	Х	Х		X	If patient wants to	
drug administration		^							continue open label	
Study drug compliancy assessment				Х	Х			Х	X	
Dispense subject diary		Х		Х	Х	Х		Х	Х	
α KCCQ, SF-36 and PAH-SYMPACT questionnaires		Х			Х	Х			Х	
AE Assessment			Х	Х	Х	Х	Х	Х	х	Х
Review of concomitant medications	Х		X	X	X	X	X	X	x	
Interval History Assessment			Х	Х	Х	Х	Х	Х	Х	Х

- Sponsor: [name]
- ∞ If subject has had an echocardiogram within the past year, we may not obtain during screening.
- Spirometry lung function test may not be needed at baseline visit if results are available within 6 months from enrollment.
- ↑ A screening RHC may not be performed if a RHC was completed within 12 months from enrollment per PI discretion.
- 3 Micromanometry is optional and completed during RHC.
- n Insulin-dependent diabetics will not receive the IVGTT.
- α At month 3 and month 6 of open label period, subjects will complete three questionnaires, six-minute walk test and NT-proBNP blood draw.

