## **PROTOCOL SYNOPSIS**

Protocol Title:	Oral Nitrite in Patients with Pulmonary Hypertension and Heart Eailure with Preserved Ejection Fraction (PH-HFpEF)
Protocol Number:	PRO16110594
NCT Number:	03015402
Version # and Date:	Version 14.0/February 14, 2022
Clinical Phase:	Phase II clinical investigation
Investigational Drug:	Oral Nitrite (NO 2 )
Trial Site:	Single-Center Trial
Sponsor:	[name] Professor of Medicine Chair, Department of Medicine University of Pittsburgh
Investigator:	[name], Assistant Professor of Medicine University of Pittsburgh UPMC PACCM
Sub-Investigators:	[name] [name] [name] [name] [name] [name] [name] [name]
Study Monitor:	[name] Chairman, Department of Medicine University of Pittsburgh School of Medicine [name]
Research Facilities:	UPMC Presbyterian Hospital [name]
Clinical Laboratories:	University of Pittsburgh Medical Center [name]

Page **4** of **47 V14.0 02/14/2022** 

Manufacturer:	Triangle Compounding Pharmacy, Inc. [name] University of Iowa Pharmaceuticals Iowa City, Iowa 52242
Study Rationale:	A strong foundation of knowledge supports that nitrite, as a source of nitric oxide (NO), can prevent and reverse experimental pulmonary hypertension.
Study Hypothesis:	
 
We hypothesize that:
 
NO2 40mg given orally three times a day for 10 weeks will improve hemodynamics, with a reduction in peak mean pulmonary arterial pressure (mPAP) during submaximal exercise as compared to placebo (primary endpoint), as well as resting mPAP, pulmonary capillary wedge pressure (PCWP) at rest and with submaximal exercise, right atrial pressure at rest and with submaximal exercise, and an increase in pulmonary artery compliance at rest and with submaximal exercise (all secondary endpoints).
 
NO2 40mg given orally three times a day for 10 weeks will improve exercise performance, including exercise time and maximal oxygen consumption during maximal and submaximal exercise as compared to placebo (secondary endpoint).
 
NO2 40mg given orally three times a day for 10 weeks will improve insulin sensitivity, fasting blood glucose, and HgbA1c, compared to placebo (exploratory endpoint).
 

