## 2.4.9 Intravenous Glucose Tolerance Test (IVGTT)

This visit will take place in the Montefiore CTRC. This test will occur at least 48 hours after the last exercise bout to account for the effects of acute exercise on insulin resistance. Subjects will be asked not to drink or eat anything other than plain water for 8 hours prior to their arrival for this visit.

Both glucose and insulin will be injected intravenously into the arm. Blood samples will be taken over the course of 3.5 hours, totaling about 15 1/2 tablespoons.

The IVGTT is considered a gold-standard test to measure insulin secretion and sensitivity. It has been standardized and used worldwide for more than 20 years. In our study, the expected duration is 180 mins after the test is started with an IV glucose bolus of 0.3g/kg. After the glucose bolus, a small dose of human regular insulin is given IV to moderate the plasma glucose rise. The insulin dose is 25 mUnits/Kg body weight. Patients taking oral hypoglycemics may be asked to hold those medications the morning of the IVGTT but can resume taking them following the completion of the IVGTT the same day.

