#### 2.6.2 Secondary Endpoints

Secondary endpoints:

- 1.The differences in 6MWT with Borg dyspnea scale assessments and pulse oxygen saturation measurements
- 2. RHC hemodynamics (right atrial pressure, pulmonary capillary wedge pressure, pulmonary artery pressures and resistance, pulmonary artery compliance, cardiac output, diastolic pressure gradients, and transpulmonary gradient)
- 3. Doppler-echocardiography
- 4. NT-proBNP plasma levels

- 5. NYHA functional classification changes
- 6. NO2 metabolites
- 7. Endurance exercise time (ET), changes in CPET measurements taken at isotime (oxygen consumption [VO2, L/min], minute ventilation [VE, L/min], ventilatory equivalent [VE/VO2], dead space to tidal volume ratio [Vd/Vt], Borg dyspnea and leg score, and changes in time constants for increases of Vt, respiratory rate [RR], VE, and heartrate).
- 8. Changes in fasting glucose and insulin sensitivity

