#### 3.3 EXCLUSION CRITERIA

Subjects meeting any of the exclusion criteria at baseline will be excluded from participating in study.

- Age less than 18 years
- SBP > 170 or < 110 mmHg
- DBP > 95 or < 60 mmHg
- Hemoglobin A1C > 10
- Positive urine pregnancy test or breastfeeding
- Ejection Fraction < 40%
- Dementia
- End-stage malignancy
- Major cardiovascular event or procedure within 6 weeks prior to enrollment
- Severe valvular disease
- Known chronic psychiatric or medical conditions that may increase the risk associated with study participation in the judgement of the investigator would make the subject inappropriate for entry into this study
- Smoker
- Hemoglobin < 9 g/dL
- Serum creatinine > 3.0 mg/dL
- Recent (<3 months) addition or change in dosing of hormonal contraceptive medications (OCP, IUD, DepoProvera)
- Receipt of an investigational product or device, or participation in a drug research study within a period of 15 days;
- RHC < 2 weeks from study screening RHC unless clinically indicated

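### Insulin sensitivity is measured only by IVGTT, which eligible insulin-dependent patients never receive, yet the blanket imputation and ITT rule makes no exception for it, and the planned change from baseline has no baseline IVGTT

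*Combined protocol and SAP*

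**What the plan says.** **The endpoint.** Section 2.6.2 lists as secondary endpoint 8 "Changes in fasting glucose and insulin sensitivity". The endpoint list in the Synopsis does the same, but the Synopsis hypotheses label insulin sensitivity exploratory. Hypothesis 2 in section 1.2 names insulin resistance among the expected improvements.

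**The instrument.** Section 2.4.9 says "The IVGTT is considered a gold-standard test to measure insulin secretion and sensitivity". No other measure of insulin sensitivity is described. The blood panel at the two testing visits reads "Blood samples: fasting glucose, comprehensive metabolic panel, hemoglobin A1C, fasting lipid profile, PT/PTT, complete blood count, platelet and differential, and NT-proBNP". Fasting insulin is absent from it, and also from the screening and cross-over panels and from section 2.4.6, so no fasting index is provided for.

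**Who is tested, and when.** The footnote to Table 1 (section 2.3.6) states "Insulin-dependent diabetics will not receive the IVGTT". The visit list in section 2.3.3 marks the test as optional for the rest. Table 1 schedules it at Week 10 and end of treatment (EOT) only.

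**Who is eligible.** The only glycaemic exclusion in section 3.3 is "Hemoglobin A1C > 10". Insulin use is not an exclusion.

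**How it is analysed.** Section 2.8.1 states "In all analysis, missing data will be imputed and sensitivity analysis with imputed data will be performed. All analyses will be performed by ITT approach". It compares secondary outcomes as differences between baseline and follow-up, and also plans mixed-effect models for them. The only stated exemption from imputation is for safety data (section 6.2.1).

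**The concern.** The schedule and the analysis rule do not fit together for this endpoint, in two ways.

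First, an insulin-dependent patient has no insulin-sensitivity value in either period, by design. A rule that imputes missing data in all analyses and keeps every randomised patient would have to create both values, and the only source is patients who do not need insulin. No IVGTT value from an insulin-dependent patient will exist to check that model.

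Second, the comparison named for secondary outcomes needs a baseline value, and no IVGTT is scheduled before treatment or at the cross-over visit.

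At stake is whether a reported effect on insulin sensitivity describes patients in whom it was measured, and whether its stated precision reflects the number actually tested.

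**Working it through.** The protocol gives no sample size, power or missing-data figure for insulin sensitivity, so there is no stated figure to reproduce.

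**Step 1. Can the planned quantities be obtained?**

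| Patient group | IVGTT at baseline or cross-over | IVGTT at Week 10 and EOT | Nitrite vs placebo difference | Change from baseline |
|---|---|---|---|---|
| Insulin-dependent | none | never | not measurable | not measurable |
| Others, both tests done | none | both | measurable | not measurable |
| Others, one test done | none | one | only through a model | not measurable |
| Others, both declined | none | none | not measured | not measurable |

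The last column is empty throughout. The only comparison the schedule supports is Week 10 against EOT, which in a crossover is nitrite against placebo. Fasting glucose is scheduled at screening, Week 10, cross-over and EOT, so this gap does not affect it.

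**Step 2. Which untested patients are a problem for imputation?** Decliners who are not insulin-dependent belong to the population that is tested, so treating their values as missing at random can be reasonable. Insulin-dependent patients are absent because of a characteristic related to the outcome, and none of them is observed. For them any imputation is extrapolation.

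**Step 3. Size if single filled-in values are counted as data.** Inputs: N = 26 randomised (Synopsis). The untested number is an assumption of 3, 5, 8 or 10, that is 3/26 = 12% to 10/26 = 38%. A two-sided 5% level is also assumed.

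Let n = 26 − untested, and let each tested patient have one nitrite-minus-placebo difference with standard deviation s. Filling the other N − n differences with the mean leaves the mean unchanged and shrinks the standard deviation to s√[(n−1)/(N−1)]. The t statistic is therefore multiplied by

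k = √[N(N−1) / (n(n−1))].

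The test rejects when the true t on n−1 degrees of freedom exceeds 2.060/k in absolute value, where 2.060 is the 97.5% point of t on 25 degrees of freedom.

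| Untested | n | k | 2.060/k | Null rejection, formula |
|---|---|---|---|---|
| 3 | 23 | √(650/506) = 1.133 | 1.817 | 8.3% |
| 5 | 21 | √(650/420) = 1.244 | 1.656 | 11.3% |
| 8 | 18 | √(650/306) = 1.457 | 1.413 | 17.6% |
| 10 | 16 | √(650/240) = 1.646 | 1.251 | 23.0% |

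The formula ignores sequence. Simulating the two-sequence crossover (13 per sequence, no treatment effect, 5,000 trials) gives 8.6%, 11.8%, 17.8% and 23.8% when the sequence mean is filled in, and 8.3%, 10.0%, 14.6% and 18.0% when one random draw is filled in. Using tested pairs only gives about 5% throughout.

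**Step 4. What the tested patients can show.** For a paired crossover test on n−2 degrees of freedom, solve P(noncentral t with noncentrality δ√n > t₀.₉₇₅,ₙ₋₂) = 0.80, where δ is the mean difference divided by the standard deviation of the within-patient differences. The detectable δ is 0.57 if all 26 are tested, and 0.61, 0.65, 0.70 and 0.75 with 23, 21, 18 and 16 tested.

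**The case against.** Several arguments on the other side are good, and most limit the point rather than remove it.

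- *The imputation sentence is ambiguous.* It may mean that imputed data feed only a sensitivity analysis, and a test that the schedule rules out may be regarded as not applicable rather than missing. That is a fair reading. But the sensitivity analysis would then contain the same extrapolation, and the ITT sentence still has no defined meaning for patients who are never tested.
- *Mixed models are planned.* A likelihood-based mixed model needs no imputation, and a patient without any value adds nothing to it. This stands, and it is a good route to the fix. It does not override a rule written for all analyses.
- *The error rates are not the plan's.* This stands. No imputation method is named, so a reader who infers that the plan inflates the type I error goes further than the text. Multiple imputation would keep the error rate in order, though it could not supply information about insulin-dependent patients.
- *Decliners are different.* This stands. The IVGTT is a separate item, paid separately, at each of Week 10 and EOT (section 7.2), so a decliner may still have one value.
- *The endpoint is minor.* This stands. It is unpowered, the Synopsis hypotheses call it exploratory, and fasting glucose covers the other half of endpoint 8.

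A reader might also infer that section 2.3.3 contradicts itself by saying that the IVGTT will be performed while listing it as optional. The first statement says where the test takes place, so there is no conflict.

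**Conclusion.** The point holds as a mismatch between schedule and analysis for one non-primary endpoint. Two parts rest on the text alone. Eligible insulin-dependent patients cannot have an insulin-sensitivity value, yet no rule exempts them from imputation or from the all-randomised analysis. And the baseline-to-follow-up difference cannot be computed from measured IVGTT data for any patient.

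The size is conditional. Null rejection of roughly 8% to 24% assumes that 3 to 10 of 26 patients are untested, that both their values are filled in once, and that these are counted as observed. The documents give neither insulin use nor refusal rates. Under proper multiple imputation the inflation goes and the extrapolation remains.

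A reader might infer that the protocol claims an insulin-sensitivity effect for every randomised patient. It makes no such statement; that breadth would follow only from applying its ITT sentence literally. The primary endpoint is unaffected. Priority: low.

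**What to change.** In sections 2.6.2 and 2.8.1:

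1. Define an IVGTT analysis set: randomised patients who are not insulin-dependent and have at least one IVGTT.
2. State that, for this endpoint, insulin-dependent patients are outside the imputation rule and the all-randomised rule.
3. Replace the baseline difference, for this endpoint, by nitrite against placebo from the Week 10 and EOT values. Use either a paired crossover analysis or the mixed model already planned, which lets patients with one value contribute.
4. Report the number tested in each sequence, with one and with two tests, because uptake is decided after randomisation.
5. Limit the conclusion to non-insulin-dependent patients, and keep fasting glucose as the glycaemic outcome for all randomised patients.
6. Give the endpoint one rank: reconcile exploratory in the Synopsis hypotheses with secondary in the two endpoint lists.

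The cost is a few sentences, with no new procedure and no change to who is tested. The downside is a smaller stated n and a narrower claim.
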